8.3 VISIT 3: 7-DAY FOLLOW-UP (± 3 DAYS)

To allow the Investigator's assessment of the subject's progress, the subject will be contacted by the Investigator for a telehealth appointment and interviewed/examined to assess the following:

- Numerical Rating Scale (NRS) pain score – *this pain survey must be administered prior to performing the other visit assessments to prevent information from these assessments biasing the subject's responses.*
- New or updated adverse events, if applicable
- Current work status
- Review of concomitant medications
- Current body temperature (for telehealth visits, the patient will take their temperature during the visit while being observed and display thermometer reading for the Investigator to confirm and record)

8.4 VISIT 4: 30-DAY FOLLOW-UP (\pm 10 DAYS)

To allow the Investigator's assessment of the subject's progress, the subject will be contacted by the Investigator for a telehealth appointment and interviewed/examined to assess the following:

- Numerical Rating Scale (NRS) pain score – *this pain survey must be administered prior to performing the other visit assessments to prevent information from these assessments biasing the subject's responses.*
- New or updated adverse events, if applicable
- Current work status
- Review of concomitant medications
- Current body temperature (for telehealth visits, the patient will take their temperature during the visit while being observed and display thermometer reading for the Investigator to confirm and record)

8.5 OUT OF WINDOW AND MISSED VISITS

If a subject fails to participate in a scheduled study visit within the visit window defined in the study protocol but completes the visit prior to the beginning of the next visit window, that visit is considered to have been completed out of window. A protocol deviation must be documented on the appropriate eCRF.

If a subject fails to participate in a scheduled study visit within the visit window defined in the study protocol and the next scheduled study visit window opens, that visit is considered to have been missed. A protocol deviation should be documented on the appropriate eCRF.

All attempts should be made to schedule the subject for the study follow-up as soon as possible so that it is captured late rather than missed completely.

8.6 UNSCHEDULED VISITS

Subjects may be evaluated at unscheduled post-procedure visits by the Investigator or delegated staff as needed. During unscheduled in person or remote visits with the Investigator or delegated staff, the Investigator or delegate will assess the subject's progress and perform/record the following:

- Numerical Rating Scale (NRS) pain score – *this pain survey must be administered prior to performing the other visit assessments to prevent information from these assessments biasing the subject's responses.*

- New or updated adverse events, if applicable. Adverse events must be reviewed and assessed by the Investigator.
- Current work status
- Review of concomitant medications
- Current body temperature (for telehealth visits, the patient will take their temperature during the visit while being observed and display thermometer reading for the Investigator to confirm and record)

8.7 STUDY COMPLETION/DISCONTINUATION

The Primary Endpoints will be evaluated after all subjects reach their 30-Day follow-up visit. Subjects will complete study participation after their 30-Day follow-up visit.

9. DESCRIPTION OF STUDY PROCEDURES

DEMOGRAPHICS

At screening, subject baseline characteristics including, age, gender, BMI, and race/ethnicity will be recorded.

PAST MEDICAL HISTORY

At screening, each subject's medical/surgical history will be reviewed with the subject and updated if needed. Once up to date, this medical/surgical history will be used as the basis for eligibility determination.

PHYSICAL EXAMINATION

A standard physical examination will be conducted according to the site's SOC, and eligibility criteria reviewed to assess subject's suitability for study participation. The physical exam will include a review of vitals (temperature, blood pressure, pulse and respiratory rate).

PREGNANCY EVALUATION & TEST

A pregnancy evaluation will be performed on female subjects of childbearing potential prior to procedure to ensure that the subject is not pregnant. Negative pregnancy status can be based on self-reported sexual history and contraception use. An in-clinic test must be performed using urine dipstick testing when the subject thinks there is a potential that they might be pregnant.

X-RAYS

Subjects will have AP and lateral x-rays collected at the Screening Visit to rule out the possibility of a previous or existing tibial fracture. X-rays will also be ordered by the Investigator to evaluate any adverse event that may be related to a potential tibial fracture based on clinical exam and/or adverse event details provided by the subject.

NUMERICAL RATING SCALE - PAIN

The Numerical Rating Scale (NRS) is a subjective measure in which individuals rate their pain on an eleven-point numerical scale. The scale is composed of 0 (no pain at all) to 10 (worst imaginable pain). It has been shown that a composite scoring system including best, worst, and current level of pain over the last 24 hours was sufficient to pick up changes in pain intensity with maximal reliability.

WORK STATUS

A self-reported work status evaluation will be performed to determine the subject's current work status throughout the trial.

10. EARLY DISCONTINUATION SUBJECTS

10.1 LOST TO FOLLOW-UP (LTFU)

Subjects who miss the final, 30-day study follow-up will be regarded as Lost to Follow-Up. Site staff should perform and document a minimum of three attempts to contact them via phone, and one attempt to reach them via certified mail to bring them in for the final study visit prior to considering the subject LTFU. The staff should document the date and type of attempted communication.

All efforts should be made to have subjects complete all follow-up visits but only subjects that miss the 30-day follow-up will be considered LTFU.

10.2 SUBJECT WITHDRAWALS

Subjects have the right to withdraw from the clinical investigation at any time and for any reason without prejudice to their future medical care by the investigation team or investigational site. The Investigator will ask reason for their withdrawal and will record all information regarding the subject discontinuation. Per Section 7.8, subjects who withdraw consent prior to treatment will be regarded as screen failures.

A Subject may be withdrawn from the clinical investigation for reasons including but not limited to the following:

- Subjects may choose to withdraw from the clinical investigation under the terms of the Declaration of Helsinki and their consent documentation without having to give a reason;
- Any adverse event which, in the opinion of the Investigator, is related to the treatment and will endanger the well-being of the subject if treatment is continued;
- Development of any intercurrent illness(es), infection or condition(s) that might interfere with the clinical investigation;
- Non-compliance with the clinical investigation procedures deemed by the Investigator to be sufficient to cause discontinuation;
- Any problem deemed by the Investigator to be sufficient to cause discontinuation.

Regardless of the reason for withdrawal, data available for the subject at the time of withdrawal, including the reason for withdrawal, will be documented in the subject's study records. The Investigator will treat all subjects discontinued from the investigation due to an adverse event until the event resolves. A subject that has been withdrawn from the study after treatment will not be replaced.

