7.11 TREATED SUBJECTS

A treated subject is an enrolled subject who has had the OsteoProbe measurement procedure completed and a BMSi measurement was recorded. All treated subjects, including those found to be ineligible after enrollment, will be followed for the next 30 days in accordance with the Schedule of Assessments.

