10.4 USE OF DATA FROM EARLY DISCONTINUATION CASES

Study data collected previously for subjects who withdraw from the study, are discontinued from the study by the Investigator or LTFU will be included in the data analysis and clinical study report.

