18. STATISTICAL ANALYSIS PLAN

18.1 STUDY HYPOTHESIS

The primary hypothesis is that the probability of experiencing device-related Serious Adverse Events (SAE) for subjects treated with the investigational device is smaller than the performance goal of 1%. Formally, that hypothesis to be tested are:

H_0 : The expected proportion of subjects with device-related SAE up to Day 30 (p_T) is greater than or equal to the performance goal (PG) of 1.0%.

H_A : The expected proportion of subjects with device-related SAE up to Day 30 (p_T) is less than the performance goal (PG) of 1.0%.

These hypotheses may be symbolically represented as:

$$H_0: p_T \geq PG = 1.0\%$$

$$H_A: p_T < PG = 1.0\%$$

Where p_T is the device-related SAE rate for subjects treated with the investigational device.

If the Bayesian Posterior Probability that $p_T < PG$ is greater than or equal to .975, the alternative hypothesis will be accepted, and it will be concluded that the device meets the performance goal.

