OHSU (unpublished)	X	X	X	Yes
LUMC (ongoing)	X	X	X	Yes
BARWON (ongoing)	X	X	X	Yes

The summary findings are shown below Table 8.

Table 8: Informative Prior Data

Study	# Subjects	Device Related SAEs
Robert Guerri-Fernandez (2018)	40	0
Mellibovsky L, et al (2015)	52	0
OHSU	18	0
LUMC (ongoing)	110*	0*
BARWON (ongoing)	50*	0*
Total	270*	0*

*Anticipated at the time of De Novo submission

These five studies contain or will contain 270 subjects with an anticipated rate of zero subjects experiencing a device-related Serious adverse events. Given there is no variability between these studies, the data are pooled together and collectively constitute the informative prior. To be conservative, the initial assumption will only consider 215 subjects with zero device-related adverse events. The informative prior was constructed as Jeffries prior plus the data in Table 8, that is, Beta(.5 + data, .5 + data).

When there are zero device-related SAEs in 40 prospective subjects, the posterior probability will be .9765 and the device will have been shown to meet the performance goal. Therefore, only if there are zero device-related SAE's will the alternative hypothesis be accepted.

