18.5 MISSING DATA/SENSITIVITY ANALYSIS

Given the short follow-up, there is not expected to be a large amount of missing data. Detailed descriptions of the reason(s) for missingness will be provided for every missing subject and timepoint. Subjects missing data will be multiply imputed using the posterior distribution of the observed data only. Bayesian posterior summarizes will characterize best- and worst-case scenarios as sensitivity to MAR assumption necessary for the imputation model. There will be no imputation for secondary effectiveness endpoints.

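### After the one-time procedure, Section 10.2 allows withdrawals that can end SAE ascertainment before Day 30, and no section secures the primary endpoint for those subjects

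*Combined protocol and SAP*

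**What the plan says.** The Schedule of Events (Section 1.1) and Section 8.1 place the procedure at Visit 1 only. The Day 1, 7 and 30 visits are telehealth follow-up, with in-person visits as an option.

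- **Reasons for withdrawal.** Section 10.2 lists an adverse event that the Investigator considers "is related to the treatment and will endanger the well-being of the subject if treatment is continued", then "Development of any intercurrent illness(es), infection or condition(s) that might interfere with the clinical investigation", then non-compliance, and finally any problem the Investigator thinks sufficient. Subjects withdrawn after treatment are not replaced.
- **Data kept.** Section 10.2 documents what is available when the subject leaves. On what enters the analysis and the report, Section 10.4 says: "Study data collected previously for subjects who withdraw from the study, are discontinued from the study by the Investigator or LTFU will be included". Section 14.3.2 documents new SAEs only up to the last study visit.
- **Follow-up.** Section 7.11 states: "All treated subjects, including those found to be ineligible after enrollment, will be followed for the next 30 days". Section 7.10 says the same of all enrolled subjects, with enrollment set at delivery of the local anesthetic.
- **Adverse events already recorded.** Sections 10.2, 14.3.1 and 14.4 provide for treatment or follow-up until the event resolves or, in the latter two, no further improvement is expected or the subject is lost to follow-up. The CEC adjudicates all of them (Section 14.5).
- **Missing data.** Section 18.5: "Subjects missing data will be multiply imputed using the posterior distribution of the observed data only". Best- and worst-case summaries probe the missing-at-random assumption.
- **Success.** If the posterior probability that the device-related SAE rate is below 1% "is greater than or equal to .975, the alternative hypothesis will be accepted" (Section 18.1). Sections 18.2 and 18.4 add that this requires zero events in 40.

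**The concern.** The withdrawal reasons read as if treatment were ongoing. Here nothing remains to be continued after Visit 1, so the related-event reason has no clear meaning from then on. The other reasons remove the subject from the investigation itself, which by then consists only of safety observation.

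The reasons may also be informative. Section 4.1 lists soft tissue infection, bone infection and bone fracture among the device and procedure risks. A subject withdrawn for an infection or an interfering condition may be at higher risk of the primary endpoint than those who stay, and missing-at-random imputation from the observed subjects ignores this.

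The endpoint is the only one formally tested, and a single event decides the result. One unobserved event therefore matters more here than in most trials of this size.

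**Working it through.** **Inputs.** Performance goal 1%, threshold .975 and N = 40 (Sections 18.1 and 18.2). The prior is Jeffreys plus the historical data (Section 18.2): 0 events in 215 subjects as the working assumption, 0 in 270 as anticipated at De Novo submission. The documents give no withdrawal rate, so one withdrawal is assumed, with 1 to 4 as a range.

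**Step 1: the plan's own figure.** With h prior subjects and x events in 40, the posterior is Beta(.5 + x, .5 + h + 40 − x), evaluated below .01.

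| Prior | x = 0 | x = 1 |
|---|---|---|
| h = 215 | .9765 | .8368 |
| h = 270 | .9875 | .8989 |

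The stated .9765 reproduces. One observed event fails the test under either prior.

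**Step 2: chance that one withdrawn subject is imputed with an event.** Let 39 subjects be observed without events. The predictive probability is .5 divided by the total Beta weight. Section 18.5 does not say whether the prior data belong to the imputation posterior, so both readings are shown.

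- Trial data only: .5/(1 + 39) = .5/40 = .0125, so event-free in 98.75% of draws.
- Prior included, h = 215: .5/(1 + 215 + 39) = .5/255 = .0020, so event-free in 99.8%.
- Prior included, h = 270: .5/(1 + 270 + 39) = .5/310 = .0016, so event-free in 99.8%.

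**Step 3: posterior averaged over imputations.** Section 18.5 gives no combining rule, so averaging is assumed. With w from Step 2 and P0, P1 from Step 1, the average is (1 − w)·P0 + w·P1.

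| Imputation reading | h = 215 | h = 270 |
|---|---|---|
| Trial data only | .9875 × .9765 + .0125 × .8368 = .9747 (just misses) | .9875 × .9875 + .0125 × .8989 = .9864 (passes) |
| Prior included | .9980 × .9765 + .0020 × .8368 = .9762 (passes) | .9984 × .9875 + .0016 × .8989 = .9873 (passes) |
| True event observed instead | .8368 (fails) | .8989 (fails) |

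**Step 4: more withdrawals, h = 215, no observed events.**

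| Withdrawn | Trial data only | Prior included | Worst case |
|---|---|---|---|
| 1 | .9747 | .9762 | .8368 |
| 2 | .9729 | .9759 | .5975 |
| 3 | .9708 | .9757 | .3523 |
| 4 | .9686 | .9754 | .1736 |

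The trial-data-only reading fails throughout and the prior-included reading passes throughout. The unstated choice of imputation posterior therefore settles the result on its own.

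**Step 5: which events are lost.**

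- *Already serious and device-related before withdrawal:* collected, included under Section 10.4 and adjudicated. No gap.
- *Recorded before withdrawal, becoming serious afterwards:* Section 14.3.1 follows it and requires updates in the EDC, but Section 10.4 commits only to including data collected previously. Whether the worsening counts toward the endpoint is unclear.
- *New event after withdrawal and before Day 30:* no section provides for its collection. This is the clear gap.

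**The case against.** The safeguards are real. A reader might infer that a subject withdrawn with a site infection and later hospitalised simply disappears from the endpoint. The documents do not support that: the infection is already a recorded adverse event, withdrawal is not among the stopping points for its follow-up in Section 14.3.1, the CEC can reclassify its seriousness and relationship, and the Primary Analysis Set (Section 18.3.1) keeps the subject. Only the link from a later worsening to the endpoint is left open.

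A reader might also infer that withdrawn subjects are counted as event-free, or that the plan is biased toward success whatever the details. Neither follows. Section 18.5 specifies multiple imputation with best- and worst-case summaries, and on the 215-subject, trial-data-only reading one withdrawal gives .9747, so the test fails anyway.

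It is fair to add that the infection and illness reason applies only where the condition might interfere with the investigation, and that Section 10.2 can be read as an exception to Sections 7.10 and 7.11. The passages are in tension and need reconciling; they are not a flat contradiction. The harmful sequence (a withdrawal, then a new related SAE before Day 30, among 40 subjects) may also be rare.

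Two things survive. No section secures Day 30 status for a new event after withdrawal. The worst-case summary would display the uncertainty (.8368 for one subject), but it has no stated role in the decision and cannot recover the outcome.

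**Conclusion.** The concern holds in a limited form. Section 10.2 permits withdrawal from safety observation after a single procedure, for reasons that may be related to the device. A new device-related SAE after that point would go uncollected, and Section 18.5 would replace it with a draw that is event-free about 98.75% to 99.8% of the time.

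With one withdrawal and averaging over imputations, a missed event turns failure into success if the prior is included in the imputation or if the 270-subject prior is used: .9762, .9864 or .9873, against .8368 or .8989 with the event observed. With 215 prior subjects and trial data only, the risk runs the other way, since even an event-free withdrawn subject can sink the trial at .9747. The direction thus depends on choices the plan leaves open, and the expected size cannot be given without a withdrawal rate. This should be fixed as a cheap improvement; it does not show that the test is invalid.

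**What to change.** - **Section 10.2:** state that after enrollment (Section 7.10), discontinuation by the Investigator does not end AE and SAE ascertainment through Day 30, and that only the subject's withdrawal of consent does. Reconcile the wording with Sections 7.10, 7.11 and 14.3.1, and clarify what the related-event reason means once the procedure is over.
- **Section 10.4:** include all safety data obtained through Day 30, including data obtained after discontinuation and any worsening of an event recorded earlier.
- **Section 18.5, for the subjects still missing:** name the imputation posterior (with or without the prior data), the rule for combining imputations, and the role of the worst-case result in the decision.

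The cost is protocol and SAP wording plus a few extra contacts with discontinued subjects, at visits that are already scheduled and mostly by telehealth. The change concerns data collection and alters no clinical care.

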10.3 DOCUMENTATION OF EARLY DISCONTINUATION

In every instance where a subject does not complete the study, the Investigator will document the primary reason for discontinuation in the subject's records.

All subjects are free to withdraw from participation at any time, for any reason, specified or unspecified, and without prejudice. However, if a subject expresses a desire to withdraw their consent for the study, the site should attempt to obtain written documentation for their study records.

For subjects that are discontinued by the Investigator, the Investigator must notify them of their discontinuation from the study in writing.

10.4 USE OF DATA FROM EARLY DISCONTINUATION CASES

Study data collected previously for subjects who withdraw from the study, are discontinued from the study by the Investigator or LTFU will be included in the data analysis and clinical study report.

10.5 ONGOING TREATMENT FOR EARLY DISCONTINUATION CASES

Subjects who withdraw voluntarily or are discontinued by the Investigator will remain eligible for SOC treatment by the Investigator and study staff.

11. EARLY DISCONTINUATION: STUDY

11.1 PROCEDURE FOR SUSPENSION OR EARLY TERMINATION

The Sponsor may suspend or prematurely terminate this clinical investigation either at the investigational site. An Investigator, IRB, or regulatory authority may suspend or prematurely terminate participation in this clinical investigation at the investigational site for which they are responsible.

If suspicion of an unacceptable risk to subjects arises during the clinical investigation, or when so instructed by the IRB or regulatory authorities, the Sponsor will suspend the clinical investigation while the risk is assessed. If an unacceptable risk is confirmed, the Sponsor will terminate the clinical investigation.

The Sponsor will consider terminating or temporarily suspending the participation of the investigational site or Investigator if monitoring or auditing identifies serious or repeated deviations on the part of an Investigator.

If suspension or premature termination occurs, the terminating party will justify its decision in writing and promptly inform the other party.

If suspension or premature termination occurs:

The Sponsor will remain responsible for providing resources to fulfill the obligations from this protocol and existing agreements for following the subjects enrolled in the clinical investigation, and the Investigator or authorized delegate will promptly inform the enrolled subjects at his/her investigational site.

If the study is terminated, Active Life Scientific, Inc. must comply with all applicable government regulations and the protocol-required subject follow-up. If discontinuation of the study should occur, the Investigator must return all clinical investigation materials (including devices) to the Sponsor, and provide a written statement to the IRB explaining the reasons for the premature termination. All applicable clinical investigation documents shall be subject to the same retention policies, as detailed in Section 19.

11.2 PROCEDURE FOR RESUMING THE CLINICAL INVESTIGATION AFTER TEMPORARY SUSPENSION

When the Sponsor concludes an analysis of the reason(s) for the suspension, implements the necessary corrective actions, and decides to lift the temporary suspension, the Sponsor will inform the relevant parties of the rationale and provide them with the relevant data supporting this decision. Concurrence will be obtained from the IRBs and, where appropriate, regulatory authorities before the clinical investigation

resumes. If subjects have been informed of the suspension, the Investigator or authorized delegate will inform them of the reasons for resumption.

